15.1.4.3. Pattern Mixture Model with Placebo-based Multiple Imputation

A pattern-mixture model using a placebo-based multiple imputation method will be performed as a second sensitivity analysis to explore the robustness of the MMRM results for the primary and key secondary efficacy variables for the ITT population. This method was based on methodology proposed by Ratitch and O'Kelly (Ratitch & O'Kelly, 2011). The assumption that efficacy profiles of dropouts after discontinuation are similar to those of placebo patients is considered conservative because this methodology tends to minimize the difference between SM-13496 and placebo groups. If the results of this analysis are in line with the primary efficacy results, then it can be confidently concluded that the primary analysis results are robust.

Using this method, missing data after dropout will be imputed based on placebo group data using multiple imputation methodology for all patients (including active treatment patients).

The steps to implement this sensitivity analysis are as follows:

1. 1000 datasets will be generated where missing data at intermediate visit(s) will be imputed for each treatment group using non-missing data from all patients within the treatment group by a Monte Carlo Markov Chain (MCMC) imputation model using the MCMC statement in the SAS PROC MI procedure. As a result, each dataset will only have missing ending data, or a monotone missing data pattern.
2. For each dataset from Step 1, missing ending data will be imputed based on information from the placebo group. As a result, 1000 imputed complete datasets will be generated.
 - Missing data at the first post-baseline visit will be imputed by a regression imputation model using the SAS PROC MI procedure with the REGRESSION option in the MONOTONE statement.
 - The SAS PROC MI procedure will use data from all placebo patients as well as SM-13496 patients with missing data at the visit (i.e., only those that need imputation at the visit). Because patients

Document: K:\DSP\SM-13496\KVA95374\Biostatistics\Documentation\SAP
 Author: [REDACTED] Version Number: 1.0
 Version Date: 30MAR2017

Template No: CS_TP_BS016 – Revision 3 Reference: CS_WI_BS005
 Effective Date: 01May2012

Copyright © 2012 [REDACTED] All rights reserved. [REDACTED] Unauthorized use, disclosure or reproduction is strictly prohibited.

from SM-13496 groups without missing data at the visit are excluded from this step, they will not contribute to the estimation of the imputation model for the visit.

- Repeat for all other visits sequentially. Patients whose missing data were imputed at previous visits will contribute to the imputation for the next visit.
 - The regression imputation model includes an intercept and the slopes of the measurements from all previous visits (Allison, 2010).
3. Analyze each imputed complete dataset
 - The MMRM model used for the primary and key secondary efficacy variables will be utilized for each imputed dataset.
 4. Combine estimates from the results of each MMRM model
 - SAS MIANALYZE procedure will be used to combine the results.

The results of the placebo-based multiple imputation analysis will be compared with the MMRM results for the primary and key secondary efficacy variables to support the robustness of the MMRM results.

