3.5 Sample size

The target number of the randomized patients is 501 (ie, 167 patients per treatment group)

Rationale

The sample size for the study has been determined by a Monte-Carlo simulation using the Statistical Analysis Software (SAS Version 9.2, SAS Institute). The sample size calculation is based on the number of patients required for the primary analysis in the intention-to-treat (ITT) population, where the primary analysis is performed on the change from baseline in the MADRS total score at Week 6. Hochberg procedure will

be utilized for the multiplicity adjustment to the multiple comparisons between each SM-13496 (20-60 and 80-120 mg/day) group and the placebo group.

A common effect size of 0.35 (ie, an intergroup difference in change from baseline of 3.5 with a standard deviation of 10) in the MADRS total score for both SM-13496 groups over placebo group was used for estimating the sample size. A sample size of 161 per group for a total of 483 patients was estimated to yield a complete power (probability of rejecting 2 null hypotheses) of 80%, with a one-sided 2.5% significance level using Hochberg procedure for multiplicity adjustment. Considering the possibility of patients who are randomized but who do not provide any post-baseline MADRS total score, the total sample size will therefore be 501 patients or 167 patients per treatment group.

The assumed effect size of 0.35 has been determined based on the PREVAIL 2 study of which study design is similar to that of the present study. In the PREVAIL 2 study, the sample size had been calculated with effect sizes of 0.39 for both SM-13496 groups (20-60 and 80-120 mg/day), and as a result, effect sizes were 0.45 for both SM-13496 groups over the placebo group on the change from baseline at Week 6 (last observation carried forward [LOCF]) in the MADRS total score. The result of the PREVAIL 2 study is shown in Table 2.

Table 2 Change from baseline in the MADRS total score at Week 6 (LOCF) – Analysis of Covariance –, Intention-to-Treat population, in the PREVAIL 2 study

	SM-13496 20-60 mg/day (N=161)	SM-13496 80-120 mg/day (N=162)	Placebo (N=162)
LS mean (SE)	-13.9 (0.80)	-13.9 (0.78)	-9.5 (0.79)
Inter-treatment difference vs. placebo (SE)	-4.5 (1.10)	-4.4 (1.10)	
Effect size	0.45	0.45	

LS means are from an analysis of covariance (ANCOVA) with treatment and pooled study site as fixed factors and baseline value as a covariate.

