5.1. INTENTION-TO-TREAT POPULATION (ITT)

The ITT population will consist of all patients who fulfill the following conditions:

- Patients who are randomized and take at least one dose of the study drug in the treatment phase, regardless of any protocol deviations
- Patients who have baseline and at least one post-baseline evaluable MADRS total score (this means that all components of the MADRS questionnaire must be completed).

For analyses and displays based on ITT, patients will be classified according to randomized treatment.

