5.2. PER PROTOCOL POPULATION [PP]

The PP population will consist of patients from the ITT population who fulfill the following conditions:

- Patients who fulfill the inclusion criteria (3) to (7), and (10) (see Protocol Section 4.1.1) and do not meet any of the exclusion criteria (1), (5) to (12), (18) to (21), and (28) (see Protocol Section 4.1.2)
- Patients who have been treated for 14 days or longer
- Patients who receive 75% to 125% of study treatment in the treatment phase

Document: K:\DSP\SM-13496\KVA95374\Biostatistics\Documentation\SAP

Author: [REDACTED]

Version Number:

1.0

Version Date:

30MAR2017

Template No: CS_TP_BS016 – Revision 3

Reference: CS_WI_BS005

Effective Date: 01May2012

Copyright © 2012 [REDACTED] All rights reserved.

The contents of this document are confidential and proprietary to [REDACTED]. Unauthorized use, disclosure or reproduction is strictly prohibited.

- Patients who do not receive any psychotropic medication other than antiparkinson drugs, anxiolytics, and hypnotics during the treatment phase
- Patients who have no important protocol deviations as determined by a blinded data review

The first 3 conditions will be verified using SAS programming. A medical review will be conducted by [REDACTED] or Sponsor Medical team to identify psychotropic medications. A review sheet will be provided for identifying medications and the completed sheet will be incorporated into SAS derived datasets.

For identifying other important protocol deviations, a blind data review meeting will be convened with representatives from [REDACTED] and the Sponsor to determine whether the deviations require the patient to be removed from the PP population.

For analyses and displays based on PP, patients will be classified according to randomized treatment.

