15.2. SECONDARY EFFICACY

The secondary efficacy analyses will be performed for the ITT population for all secondary variables, and the PP population where specified.

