SOLUTION COVB DDFM = KR;
RANDOM INTERCEPT DAY /SUB=USUBJID TYPE=UN G;
RUN;

b. Multiple Imputation

NOTE: Placebo based imputation

```
PROC MI
VAR SITEGR1N SCORE_1 SCORE_2 SCORE_3 SCORE_4 SCORE_5 SCORE_6
SCORE_7;
BY TRT01PN;
MCMC CHAIN=MULTIPLE IMPUTE=MONOTONE;
RUN;

%MACRO MI_IMP(INDATA=, ANVIS=, SEED=, VAR1=, VAR2=, OUTDATA=);
DATA EFF_MONO_IMP EFF_MONO_REST;
SET &INDATA;
IF TRT01PN IN (2,3) AND LASTVIS >=&ANVIS THEN OUTPUT
EFF_MONO_REST;
ELSE OUTPUT EFF_MONO_IMP;
RUN;

PROC SORT DATA= EFF_MONO_IMP;
BY _IMPUTATION_;
RUN;

PROC MI DATA=EFF_MONO_IMP OUT=EFF_REG_IMP NIMPUTE=1 SEED=&SEED
MINIMUM=0 MAXIMUM=60;
VAR &VAR1 &VAR2;
BY _IMPUTATION_;
MONOTONE REGRESSION(&VAR2= &VAR1 / DETAILS);
RUN;

DATA &OUTDATA;
SET EFF_MONO_REST EFF_REG_IMP;
RUN;

PROC DATASETS;
DELETE EFF_MONO_IMP EFF_MONO_REST EFF_REG_IMP;
RUN;
%MEND MI_IMP;
```

Document: K:\DSP\SM-13496\KVA95374\Biostatistics\Documentation\SAP
Author: [REDACTED] Version Number: 1.0
Version Date: 30MAR2017

Template No: CS_TP_BS016 – Revision 3
Effective Date: 01May2012

Reference: CS_WI_BS005

Copyright © 2012 [REDACTED] All rights reserved.
The contents of this document are confidential and proprietary to [REDACTED]. Unauthorized use, disclosure or reproduction is strictly prohibited.

```
%MI_IMP(INDATA=EFF_MONO, ANVIS=2, SEED=445566, VAR1=SCORE_1 SCORE_2,  
VAR2=SCORE_3, OUTDATA=EFF_IMP1);  
%MI_IMP(INDATA=EFF_IMP1, ANVIS=3, SEED=445566, VAR1=SCORE_1 SCORE_2  
SCORE_3, VAR2=SCORE_4, OUTDATA=EFF_IMP2);  
%MI_IMP(INDATA=EFF_IMP2, ANVIS=4, SEED=445566, VAR1=SCORE_1 SCORE_2  
SCORE_3 SCORE_4, VAR2=SCORE_5, OUTDATA=EFF_IMP3);  
%MI_IMP(INDATA=EFF_IMP3, ANVIS=5, SEED=445566, VAR1=SCORE_1 SCORE_2  
SCORE_3 SCORE_4 SCORE_5, VAR2=SCORE_6, OUTDATA=EFF_IMP4);  
%MI_IMP(INDATA=EFF_IMP4, ANVIS=6, SEED=445566, VAR1=SCORE_1 SCORE_2  
SCORE_3 SCORE_4 SCORE_5 SCORE_6, VAR2=SCORE_7, OUTDATA=EFF_IMP5);
```

```
DATA MI_EFF;  
  SET EFF_IMP5;  
  AVISITN=1;  
  DIFF=SCORE_2-SCORE_1;  
  OUTPUT;  
  AVISITN=2;  
  DIFF=SCORE_3-SCORE_1;  
  OUTPUT;  
  AVISITN=3;  
  DIFF=SCORE_4-SCORE_1;  
  OUTPUT;  
  AVISITN=4;  
  DIFF=SCORE_5-SCORE_1;  
  OUTPUT;  
  AVISITN=5;  
  DIFF=SCORE_6-SCORE_1;  
  OUTPUT;  
  AVISITN=6;  
  DIFF=SCORE_7-SCORE_1;  
  OUTPUT;
```

```
RUN;
```

```
ods listing close;
```

```
PROC MIXED;
```

```
  CLASS USUBJID TRT01PN AVISITN SITEGR1N;  
  MODEL      DIFF=SCORE_1      TRT01PN      AVISITN      SITEGR1N  
TR01PN*AVISITN/DDFM=KR SOLUTION CL;  
  REPEATED AVISITN /SUBJECT=USUBJID TYPE=UN;
```

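### The placebo-based imputation is limited to the ITT set, so dosed patients with a baseline MADRS but no evaluable post-baseline MADRS are in no efficacy analysis; its step 1 code also enters the site code as a continuous variable

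*SAP*

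**What the plan says.** **Population.** SAP 15.1.4.3 specifies the placebo-based imputation for the "primary and key secondary efficacy variables for the ITT population. This method was based on methodology". SAP 5.1 limits ITT to patients who are randomised, take at least one dose, and meet a further condition: "Patients who have baseline and at least one post-baseline evaluable MADRS total score". SAP 5.2 offers no wider set: "The PP population will consist of patients from the ITT population who fulfill the following conditions". SAP 15.2 adds: "The secondary efficacy analyses will be performed for the ITT population for all secondary variables", with PP where specified. The primary MMRM (15.1.3.1) and the random-effects pattern mixture model (15.1.4.2) use ITT. The LOCF ANCOVA (15.1.4.1) uses ITT and PP.

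**Expected exclusions.** Protocol 3.5 raises the sample from 161 to 167 per group for this reason: "Considering the possibility of patients who are randomized but who do not provide any post-baseline MADRS total score".

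**Imputation steps.** SAP 15.1.4.3 first fills intermediate gaps within each arm by MCMC. It then imputes the remaining scores visit by visit from placebo data, and the text begins at the first visit after baseline: "Missing data at the first post-baseline visit will be imputed by a regression imputation model". In Appendix 3 (item 3b) the first placebo-based call is "MI_IMP(INDATA=EFF_MONO, ANVIS=2, SEED=445566, VAR1=SCORE_1 SCORE_2", with `SCORE_3` as its target. The later calls target `SCORE_4` to `SCORE_7`.

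**Site.** The step 1 PROC MI uses "VAR SITEGR1N SCORE_1 SCORE_2 SCORE_3 SCORE_4 SCORE_5 SCORE_6" and then `SCORE_7`, with an MCMC statement and no CLASS statement. The PROC MIXED that analyses the imputed data lists `SITEGR1N` in CLASS.

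**The concern.** Having a post-baseline rating is a condition observed after randomisation. For an MMRM on change it costs nothing in practice, because a patient with no post-baseline value contributes no change score. An imputation that starts from baseline is different: it can supply those values. SAP 15.1.4.3 treats agreement between this analysis and the primary result as grounds for confidence that the primary result is robust. If the patients with the least follow-up are left out, that conclusion covers dropout only after a first rating.

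The code issues are secondary. The text promises a Week 1 imputation that no call carries out. Using a site label as a number lets the order of arbitrary codes influence imputed scores.

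**Working it through.** **1. Is any analysis open to these patients?** Protocol 9.2.1 and SAP 5.1 both require a post-baseline MADRS for ITT, and PP lies within ITT. Every efficacy section names one or both. So the answer is no. If dosed, these patients appear in the safety population (SAP 5.3) and in disposition (SAP 9).

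**2. The plan's own figure.** Inputs from Protocol 3.5: difference 3.5, SD 10, 161 evaluable per group, one-sided 2.5%, Hochberg, 80% power to reject both nulls. Hochberg rejects both when both one-sided p-values are at most 0.025. The two test statistics share the placebo arm, so their correlation is 0.5. Each has mean 0.35 × √(161/2) = 3.14. The probability that both exceed 1.96 is 80.4%, and a t-based simulation of 200,000 trials gives 80.2%. The stated 80% is reproduced.

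**3. The planning allowance.** 167 − 161 = 6 per group; 501 − 483 = 18; 18/501 = 3.6%.

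**4. Effect of including these patients.** Assume that those on active drug have placebo-like outcomes, so their expected difference from placebo is zero. With k such patients of 167:

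difference = 3.5 × (1 − k/167)

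| k per arm | Share | Difference | Illustrative power to reject both, n = 167 |
|---|---|---|---|
| 2 | 1.2% | 3.46 | 80.9% |
| 6 | 3.6% | 3.37 | 78.6% |
| 10 | 6.0% | 3.29 | 76.1% |

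The power column only gives scale. It treats imputed values as observed, and the plan sets no power target for a sensitivity analysis. At k = 6 the shift is 3.50 − 3.37 = 0.13 points. The design standard error is 10 × √(2/161) = 1.11, so the shift is about 0.11 standard errors.

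A harsher scenario gives the six active patients no change at all and keeps the placebo mean at −9.5 (Protocol 3.5, Table 2). The active mean is then 13.0 × 161/167 = 12.53 points of improvement, the difference 3.03 and the power 67.5%. This is not what placebo-based imputation assumes, and it penalises the active arms only.

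**5. Week 1 in the code.** The `MI_EFF` data step defines the Week 1 change as `SCORE_2` minus `SCORE_1`, so `SCORE_2` is Week 1 and `SCORE_3` is Week 2. `SCORE_2` is a predictor in the first call and the named target of none.
- ITT patient with any scheduled rating: step 1 fills earlier gaps, so Week 1 is present and starting at `SCORE_3` works.
- ITT patient whose only rating is unscheduled: SAP 5.1 does not require a scheduled rating, and SAP 6.4 keeps unscheduled values out of by-visit data. All scheduled scores are then missing, and no call is written for Week 1.
- Baseline-only patient: same gap.

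**6. Site in the code.** `SITEGR1N` is not defined. Its place in the MIXED model suggests the pooled centre, numbered 901 to 928 in SAP 7.2, Table B. In MCMC without CLASS it enters as a number. It occurs only in step 1: the placebo-based regressions omit it and the analysis model treats it as categorical. The effect is therefore confined to intermediate gaps.

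**The case against.** The strongest defence is that the population is a deliberate and consistent choice. Protocol and SAP define ITT alike, the sample size allows for the exclusion, and 15.1.4.3 sets out to test the MMRM result in ITT. That stands: the plan does not contradict itself on the population. It does not answer the point that the robustness conclusion leaves out patients with no rating after baseline.

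The excluded group is also likely to be small. Protocol 4.3.2 and 6.2.1 call for a MADRS at discontinuation, and SAP 6.4 and 6.5 map that rating to the next scheduled visit. An early leaver who attends it enters ITT. This stands, and it rules out a reading that some may be tempted by: that the excluded patients are mainly those who could not tolerate active drug. The documents give neither reasons nor a split by arm.

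A reader might also infer that this is the only analysis able to include these patients. It is not. The random-effects pattern mixture model in 15.1.4.2 takes the baseline score as a response and could admit them as dropouts.

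Finally, the Week 1 mismatch might be read as breaking the planned analysis. Within ITT it does not, apart from the patient with only an unscheduled rating.

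**Conclusion.** The point holds as a gap in a sensitivity analysis; the primary test is not affected. Dosed patients with a baseline MADRS and no evaluable post-baseline MADRS are in no efficacy analysis, so the robustness conclusion of 15.1.4.3 does not extend to them.

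The size is modest. At the planning allowance the difference moves from 3.5 to about 3.37, assuming placebo-like outcomes in those on active drug. Two considerations make that an upper planning figure. The allowance covers all randomised patients, including any never dosed (dosing starts the day after randomisation), while the group at issue is the dosed ones. And the dilution would apply to the placebo-imputed ITT estimate, which should already be below 3.5, so the further shift in points would be smaller than 0.13. The actual count could differ from the allowance. A 10% share would give 3.5 × 0.90 = 3.15, but that would be more than half of the 17.4% overall dropout reported in SAP 15.1.4.2.

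The Week 1 call has little effect in ITT but becomes necessary once baseline-only patients are included. The continuous site code is a modelling error, on the reading that `SITEGR1N` is the pooled centre. Its effect is probably small, though the documents give no figure from which to compute it.

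**What to change.** 1. Keep 15.1.4.3 in ITT as planned. Add a parallel run in all randomised, dosed patients with a baseline MADRS, analysed by randomised arm, and report the two side by side with the number of added patients per arm.
2. In Appendix 3, add a call before the present first one that imputes `SCORE_2` from `SCORE_1` (`ANVIS=1`), and pass its output to the Week 2 call. This also brings the code into line with the text.
3. Remove `SITEGR1N` from the step 1 MCMC variable list. The step 1 text does not call for site, and MCMC cannot treat it as categorical. If site is wanted in the imputation because the analysis model contains it, use a method that accepts a CLASS variable and say so in the text.

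The cost is one population flag, one macro call, one changed variable list and one extra set of output. The added sensitivity estimate would probably be slightly less favourable to active drug than the ITT version.

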15.1.4.4. Primary Analysis on Per Protocol Population

The MMRM from the primary analysis will also be performed on the PP population to obtain additional information on the robustness of results across populations.

15.2. SECONDARY EFFICACY

The secondary efficacy analyses will be performed for the ITT population for all secondary variables, and the PP population where specified.

15.2.1. SECONDARY EFFICACY VARIABLES & DERIVATIONS

15.2.1.1. Clinical Global Impressions Scale – Bipolar Version - Severity of Illness (CGI-BP-S)

The change from baseline in CGI-BP-S depression score at Week 6 is a secondary efficacy variable. The CGI-BP-S depression score, measured at Screening, Baseline, Weeks 1 to 5, and Week 6/Early Term, is a single value, clinician-rated assessment of the subject's current severity of depression and ranges from 1= 'Normal, not ill' to 7= 'Very severely ill'.

The change from baseline will be calculated as the score at Week 6 – score at baseline.

A LOCF endpoint will also be derived for CGI-BP-S. For calculation details, please see section 6.3.

Additional efficacy ANCOVA analyses will be conducted based on change from baseline in CGI-BP-S depression score at Weeks 1 – 6, and Week 6 LOCF endpoint.

15.2.1.2. Sheehan Disability Scale (SDS)

The change from baseline in SDS total score at Week 6 (LOCF) endpoint is a secondary efficacy variable. The SDS is measured at Baseline and Week 6/Early Term. Three items are self-rated using an 11-point visual analog

Document: K:\DSP\SM-13496\KVA95374\Biostatistics\Documentation\SAP

Author: [REDACTED]

Version Number:

1.0

Version Date:

30MAR2017

Template No: CS_TP_BS016 – Revision 3

Reference: CS_WI_BS005

Effective Date: 01May2012

Copyright © 2012 [REDACTED] All rights reserved.

The contents of this document are confidential and proprietary to [REDACTED]. Unauthorized use, disclosure or reproduction is strictly prohibited.

scale ranging from 0 to 10 to assess disability across three domains: work/school, social life, and family life; the three items will be summarized individually in addition to the SDS total score. The SDS total score is calculated as the sum of the 3 items and ranges from 0 (Not at all) to 30 (Extremely). If one or more items are missing at a visit, as can occur when a subject opts out of the work/school item because it does not apply, the total score will be set to missing.

15.2.1.3. Young Mania Rating Scale (YMRS)

The change from baseline in YMRS to week 6 is a secondary efficacy variable. The YMRS is collected at Screening, Baseline, Weeks 1 to 5, and Week 6/Early Term. The YMRS is an 11-item clinician-rated instrument used to assess the severity of mania in patients with a diagnosis of bipolar disorder. The 11 items are: elevated mood, increased motor activity energy, sexual interest, sleep, irritability, speech (rate and amount), language-thought disorder, content, disruptive-aggressive behavior, appearance and insight. Seven items are rated on a 5-point scale, ranging from 0 to 4, and four items are rated on a 9-point scale, ranging from 0 to 8. Ratings are based on patient self-reporting, combined with clinician observation. The YMRS total score is the sum of the 11 individual items and ranges from 0 to 60. A higher score is associated with a greater severity of mania. If one or more items are missing at a visit, the total score will be set to missing.

The change from baseline will be calculated as the score at Week 6 – score at baseline.

A LOCF endpoint will also be derived for YMRS. For calculation details, please see section 6.3.

15.2.1.4. Hamilton Rating Scale for Anxiety (HAM-A)

The change from baseline in HAM-A total score at Week 6 (LOCF) endpoint is a secondary efficacy variable. The HAM-A is used to quantify the severity of anxiety symptomatology. The HAM-A is a 14-item, rater administered questionnaire collected at Baseline and Week 6/Early Term. The 14 items are: anxious mood, tension, fears, insomnia, intellectual, depressed mood, somatic (muscular), somatic (sensory), cardiovascular symptoms, respiratory symptoms, gastrointestinal symptoms, genitourinary symptoms, autonomic symptoms, and behavior at interview. Each of the 14 items is rated on a 5-point scale, ranging from 0 (not present) to 4 (severe/disabling). The HAM-A total score is the sum of the 14 individual items and ranges from 0 to 56. A higher score is associated with a greater degree of anxiety. If one or more items are missing at a visit, the total score will be set to missing.

